4.3 Inclusion criteria

For inclusion in the study, all of the following inclusion criteria must be fulfilled. It is not permitted to waive any of the criteria for any subject.

Criteria assessed at Visit 1

1. Signed informed consent prior to any study-mandated procedure.
2. Male or female aged ≥ 18 years.

3. Insomnia disorder according to DSM-5 criteria as follows:
 - 3.1 The predominant complaint is dissatisfaction with sleep quantity or quality, associated with one (or more) of the following symptoms:
 - Difficulty initiating sleep.
 - Difficulty maintaining sleep, characterized by frequent awakenings or problems returning to sleep after awakenings.
 - Early-morning awakening with inability to return to sleep.
 - 3.2 The sleep disturbance causes clinically significant distress or impairment in social, occupational, educational, academic, behavioral, or other important areas of functioning.
 - 3.3 The sleep difficulty occurs despite adequate opportunity for sleep.
 - 3.4 The insomnia is not better explained by and does not occur exclusively during the course of another sleep-wake disorder (e.g., narcolepsy, a breathing-related sleep disorder, a circadian rhythm sleep-wake disorder, a parasomnia).
 - 3.5 The insomnia is not attributable to the physiological effects of a substance (e.g., a drug of abuse, a medication).
 - 3.6 Coexisting mental disorders and medical conditions do not adequately explain the predominant complaint of insomnia.
 - 3.7 Self-reported history of all the following on at least 3 nights per week and for at least 3 months prior to Visit 1:
 - 3.7.1 ≥ 30 min to fall asleep, and
 - 3.7.2 Wake time during sleep ≥ 30 min, and
 - 3.7.3 $sTST \leq 6.5$ h
4. ISI[®] score ≥ 15 .
5. Ability to communicate well with the investigator, to understand the study requirements and judged by the investigator to be alert and oriented to person, place, time, and situation.

Criteria assessed at Visit 3

6. Meeting all the following sleep parameters on at least 3 nights out of 7 nights on the sleep diary completed at home between Visit 2 and Visit 3:
 - 6.1 ≥ 30 min to fall asleep, and
 - 6.2 Wake time during sleep ≥ 30 min, and
 - 6.3 $sTST$ of ≤ 6.5 h
7. Usual bedtime between 21:30 and 00:30, as reported on sleep diary completed between Visit 2 and Visit 3.
8. Regular time in bed between 6 and 9 h, as reported on sleep diary completed between Visit 2 and Visit 3.
9. Meeting all the following sleep parameters on the 2 PSG nights at Visit 3:

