7.2.2 Efficacy assessments

7.2.2.1 Polysomnography

PSG data will be used to assess objective sleep parameters (WASO and LPS) as well as data on sleep architecture (sleep stages).

PSG recordings must be performed by technologists who are familiar with the recording techniques described in the investigator site operations manual for the acquisition, processing, scoring, archiving, and transfer of digital PSG data (provided by the central scoring CRO). The quality of PSG recordings is monitored and quality-controlled on an ongoing basis. Technologists must be able to follow the procedures in this manual in order to produce technically acceptable tracings. Technologists are not required to be registered PSG technologists. Technologists must receive study-specific training prior to their participation in the study. Documentation of technologists' prior experience and training, and study-specific training will be maintained at each clinical trial site. The sites and scorers that participate in this study must be certified by the CRO. The center conditions must allow an undisturbed environment and PSG recordings must be conducted in a sleep laboratory environment that meets the guidelines for sleep disorder centers [aasmnet.org].

During the Screening period, a PSG night will be performed if the subject meets all inclusion criteria and none of the exclusion criteria checked so far, and assesses AHI, PLMAI, and SpO₂. At Visit 3, the first PSG recording starts (lights off) within \pm 30 min of

usual bedtime (determined by sleep diary between Visit 2 and Visit 3); this time is then considered as the habitual bedtime and held constant (± 15 min) throughout the study. Study medication is administered 30 min (± 5 min) before the recording starts. The PSG recording is stopped after 480 min when 960 epochs of 30 seconds have been recorded. PSGs will be performed as per the visit and assessment schedule [Table 1].

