6.1.2 Secondary efficacy endpoints

The secondary efficacy endpoints of this study are measured on patient questionnaires and defined as:

- Change from baseline^a to Month 1^b in sTST.
- Change from baseline^a to Month 3^c in sTST.
- Change from baseline^a to Month 1^b in IDSIQ Sleepiness domain score.
- Change from baseline^a to Month 3^c in IDSIQ Sleepiness domain score.

sTST (in minutes) is based on the time reported by the subject in item 9 of the sleep diary i.e., the answer to the question “In total, how long did you sleep last night?”.

The Insomnia Daytime Symptoms and Impacts Questionnaire (IDSIQ) is a patient-reported outcome measure structured in 3 domains (Alertness/Cognition; Mood; Sleepiness). The IDSIQ Sleepiness domain score is based on the sum of the responses reported by the subject for 4 items: item 8, 11, 12, and 13. Item 8 score is reversed prior to summing [see Section 6.2]. The IDSIQ Sleepiness domain score can range from 0 to 40 (whole numbers only) with higher scores indicating greater burden during the daytime.

^a Baseline is the mean value based on the screening sleep diary / IDSIQ entries performed at home in the 7 days immediately preceding the first PSG at Visit 3.

^b ‘Month 1’ is the mean value based on the sleep diary / IDSIQ entries performed at home in the 7 days immediately preceding the first PSG at Visit 6.

^c ‘Month 3’ is the mean value based on the sleep diary / IDSIQ entries performed at home in the 7 days immediately preceding the first PSG at Visit 8.

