Sensitivity analysis will be performed to assess the robustness of the conclusions of the main analysis to departures from the MAR assumption. For this, models that assume missing not at random (MNAR) will be used [[Mallinckrodt 2013](#)]. These models will be based on the multiple imputation (MI) methodology [[Rubin 1987](#)] and will be specifically used to assess the bias that can result when the outcomes for subjects who discontinue differ from those who complete. Sensitivity analyses will be performed for the analysis of change from baseline in WASO, LPS, sTST and IDSIQ Sleepiness domain score, separately.

As a general approach, imputations will be performed on observed values (baseline, Month 1 and Month 3) specifying a minimum and a maximum threshold to avoid imputation of nonsensical values. The boundaries will range from 0 to 480 for WASO, LPS and sTST, and from 0 to 40 for IDSIQ Sleepiness domain score. When an intended imputed value is outside the defined boundaries, this value will be discarded, and the procedure will draw another value for imputation. The maximum number of discarded values will be set to 100 for each imputed dataset. The imputed dataset will not be produced if more than 100 values have been discarded. If more than 20% of the planned imputed datasets are not produced, the results for that analysis will not be shown as this would likely lead to unreliable conclusions. Once all the multiply-imputed datasets are produced, the change from baseline to Month 1 and Month 3 will be calculated.

In all the MI analyses described below a preliminary step will be performed to obtain a monotone missing data pattern [see Section 12.7]. That is, any non-monotone (or intermediate) missing data will be imputed using the Markov Chain Monte Carlo (MCMC) methodology [[Schafer 1997](#)] under MAR assumptions within each treatment group. This assumption is considered reasonable given that subjects are expected to miss intermediate visits due to reasons unrelated to their insomnia disorder (e.g., scheduling conflicts), or have missing intermediate values due to technical problems (e.g., PSG not fully recorded due to power outage). In addition, the proportion of non-monotone missing data is expected

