- Change from baseline (mean of the 2 PSG nights at Visit 3) to Month 1 (mean of the 2 PSG nights at Visit 6) and Month 3 (mean of the 2 PSG nights at Visit 8) in Sleep Efficiency (defined as $100 \times [\text{TST (min)} / \text{time in bed (min)}]$) where time in bed is fixed to 480 min during the PSG nights.
- Change from baseline (Visit 3) to Month 1 (Visit 6 or, if that is missing, week 4 of the questionnaire) and Month 3 (Visit 8 or, if that is missing, week 12 of the

questionnaire) in Patient Global Assessment of Disease Severity (PGA-S) scores (daytime symptoms).

- Change from baseline (Visit 3) to Month 1 (Visit 6 or, if that is missing, week 4 of the questionnaire) and Month 3 (Visit 8 or, if that is missing, week 12 of the questionnaire) in Patient Global Impression of Change (PGI-C) scores (daytime symptoms).
- Change from baseline (Visit 3) to Month 1 (Visit 6 or, if that is missing, week 4 of the questionnaire) and Month 3 (Visit 8 or, if that is missing, week 12 of the questionnaire) in PGI-C scores (night-time symptoms).
- Change from baseline (Visit 3) to Month 1 (Visit 6 or, if that is missing, week 4 of the questionnaire) and Month 3 (Visit 8 or, if that is missing, week 12 of the questionnaire) in Patient Global Impression of Severity (PGI-S) scores (night-time symptoms).

^a Baseline is the mean value based on the screening sleep diary entries performed at home in the 7 days immediately preceding the first PSG at Visit 3.

^b ‘Month 1’ is the mean value based on the sleep diary entries performed at home in the 7 days immediately preceding the first PSG at Visit 6.

^c ‘Month 3’ is the mean value based on the sleep diary entries performed at home in the 7 days immediately preceding the first PSG at Visit 8.

Section 10.1 explains how these endpoints, except for ISI[®], are derived in the event of partially missing data.

Additionally, the following PSG measurements will be summarized:

- Change from baseline (mean of the 2 PSG nights at Visit 3) to Month 1 (mean of the 2 PSG nights at Visit 6) and Month 3 (mean of the 2 PSG nights at Visit 8) in duration (min) of TST in each sleep stage (S1, S2, SWS and REM) by quarter of the night.
- Change from baseline (mean of the 2 PSG nights at Visit 3) to Month 1 (mean of the 2 PSG nights at Visit 6) and Month 3 (mean of the 2 PSG nights at Visit 8) in duration (min) from lights off to the first epoch of each sleep stage (S1, S2, SWS and REM).

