10 GENERAL STATISTICAL METHODOLOGY

10.1 Handling of partially missing data

Partially missing data for primary endpoint WASO and LPS values, and for variables like TST, number of shifts from S2, SWS or REM to S1 or awake, number of awakenings, Coding sub-test[©], SDS[©], or neurological examination, will be handled as follows: if one of the two values is missing either for baseline, Month 1 or Month 3, the single value available will be used as the mean for this time point. Otherwise, the mean value will be considered missing for that time point.

For sTST, sWASO, sLSO, IDSIQ total and domain scores, VAS scores and number of self-reported awakenings, subjects must have at least 2 days of data during each week to calculate a weekly mean. Otherwise, the mean value will be considered missing for that week.

The approaches above imply implicit imputation: missing data points are given the same value as the mean of the non-missing data points of that same time point or week.

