12.6 Handling of data when total sleep time is zero

If the TST is recorded as zero (i.e., subject did not fall asleep during the night), then:

- WASO is set as missing since subject is never at risk, and
- LPS is set as 480 minutes which is equal to the duration of time in bed.

If the sTST is recorded as zero, then similarly:

- sWASO is set as missing, and
- sLSO is set as 480 minutes.

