12.8 Time window definitions for calculating subjective endpoints

The meaning of the first PSG end date and the last PSG end date at a given visit (Visit 3, Visit 6 and Visit 8) are shown in [Table 6](#).

Table 6 Meaning of the first and last PSG end date at Visits 3, 6 and 8

Visit 3, Visit 6 and Visit 8			
First PSG		Last PSG	
Start date (evening)	End date (morning)	Start date (evening)	End date (morning)

Values falling in the following time windows will be used to calculate weekly averages for the subjective endpoints; values from PSG night will not be included:

Screening: the 7 consecutive days immediately preceding the Run-in single-blind placebo treatment start date but after PSG end date at Visit 1 (morning) (i.e., 7-day window = [Max. (Run-in single-blind placebo treatment start date – 7 days; PSG end date at Visit 1 [morning]); Run-in single-blind placebo treatment start date – 1 day]).

Baseline (Run-in period): the 7 consecutive days immediately preceding the first PSG at Visit 3, but after Run-in single-blind placebo treatment start date (i.e., 7-day window = [Max. (End date of first PSG at Visit 3 – 7 days; Run-in single-blind placebo treatment start date); End date of first PSG at Visit 3 – 1 day]). The time window for Baseline may be less than 7 days. Baseline will be missing for any subjects without a PSG at Visit 3.

Month 1: the 7 consecutive days immediately preceding the first PSG at Visit 6 (i.e., 7-day window = [End date of first PSG at Visit 6 – 7 days; End date of first PSG at Visit 6 – 1 day]). For subjects missing PSG at Visit 6, the 7-day window = [Study day 23; Study day 29].

Month 3: the 7 consecutive days immediately preceding the first PSG morning at (Visit 8 i.e., 7-day window = [End date of first PSG at Visit 8 – 7 days; End date of first PSG at

Visit 8 – 1 day]). For subjects missing PSG at Visit 8, the 7-day window = [Study day 79; Study day 85].

Run-out: the 7 consecutive days immediately following the PSG morning at Visit 9 (i.e., 7-day window = [Date of PSG morning at Visit 9 + 1 day; Min. (Date of PSG morning at Visit 9 + 7 days; Visit 10 date)]). For subjects missing PSG at V9, the 7-day window = [Treatment withdrawal period start date; Min. (Treatment withdrawal period start date + 6 days; Visit 10 date)].

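### SAP 15.3 prints four imputation bounds for five variables, so that read by position Month 3 has none, and SAP 6.1.7 caps imputed home-diary sTST at the PSG recording length (minor; sensitivity analyses only)

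*SAP*

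**What the plan says.** SAP 6.1.7 bounds imputed values so that nonsensical ones are not used: "The boundaries will range from 0 to 480 for WASO, LPS and sTST, and from 0 to 40 for IDSIQ Sleepiness domain score". A draw outside the range is discarded and redrawn. An imputed dataset is abandoned after more than 100 discards, and the results are withheld if more than 20% of datasets are lost. The same section says that the delta = 0 case of the tipping-point series corresponds to the standard MAR imputation run.

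The 480 figure comes from polysomnography. Protocol 7.2.2.1: "The PSG recording is stopped after 480 min when 960 epochs of 30 seconds have been recorded". SAP 6.3 defines PSG sleep efficiency "where time in bed is fixed to 480 min during the PSG nights".

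sTST is measured differently. SAP 6.1.2: "sTST (in minutes) is based on the time reported by the subject in item 9 of the sleep diary", averaged over home entries in the seven days before the first PSG of the visit. SAP 12.8 adds that "values from PSG night will not be included". Protocol 4.3 accepts "Regular time in bed between 6 and 9 h, as reported on sleep diary completed between Visit 2 and Visit 3", and Protocol 7.2.2.2.1 expects that range on only half of the run-in nights.

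The bounds are implemented in the SAS code of SAP 15.2 to 15.5.

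**The concern.** Section 15.3 produces the MAR reference against which the other imputation results are read. If its bound list is one entry short, the Month 3 values there are drawn without the limits that 6.1.7 prescribes, while the delta = 0 run in 15.5 has them. Two runs that the SAP treats as the same analysis would then differ for a reason unrelated to missing data. A zero floor matters most for an endpoint whose values lie near zero, which is LPS.

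For sTST the issue is the ceiling. For WASO and LPS, 480 min is a physical limit of the recording. For diary sleep at home it is not, so 6.1.7 would reject post-baseline weekly means that are high but possible.

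**Working it through.** **Source of 480.** 960 epochs × 30 s ÷ 60 = 480 min, which reproduces the protocol's figure. The upper end of the accepted home time in bed is 9 × 60 = 540 min. A mean of 480 min asleep in 540 min in bed needs 480/540 = 89% efficiency: uncommon, but not nonsensical.

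**Bound entries against variables, as printed.**

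| SAP section | Variables | Entries in each list | Effect if read by position |
|---|---|---|---|
| 15.2 | AGE BASE OBSM1 OBSM3 (4) | 4 | as intended |
| 15.3 | TRT AGEGR BASE OBSM1 OBSM3 (5) | 4: `. 0 0 0`, `. 480 480 480` | AGEGR bounded, OBSM3 not |
| 15.4, each call | AGEGR BASE and one visit (3) | 4: `. . 0 0`, `. . 480 480` | visit bounded, BASE not, one entry spare |
| 15.5 | same five as 15.3 | 5: `. . 0 0 0`, `. . 480 480 480` | as intended |

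**LPS without a floor.** Assumptions, not in the documents: normal draws, active mean m of 30 or 45 min, SD s of 25 or 40 min. The share of negative draws is Φ(−m/s).

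- 30/25: Φ(−1.2) = 11.5%
- 30/40: Φ(−0.75) = 22.7%
- 45/25: Φ(−1.8) = 3.6%
- 45/40: Φ(−1.125) = 13.0%

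To put this in minutes, the floor raises the mean of a draw by s·φ(m/s)/Φ(m/s). Take the placebo mean as 15 min higher (the planned LPS difference, Protocol 10.5) and the worst case, s = 40. The rise is 15.6 min in the active arm (mean 30) and 9.7 min in the placebo arm (mean 45). Runs with and without the floor then differ by 5.8 min per imputed value. With 3.9% imputed (the Phase 2 treatment discontinuation rate in SAP 6.1.4, used as a proxy), that is 5.8 × 0.039 = 0.23 min in the contrast, against a planned 15 min.

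**sTST with the 480 cap.** Assumptions: placebo means of 340–380 min, active 20 min higher (the planned difference), and SD of a draw of 38.6–54 min. Protocol 10.5 gives 54 but may mean the SD of change. If 54 is the SD of levels, the SD given baseline is 54√(1−r²): 46.8 at r = 0.5 and 38.6 at r = 0.7. If 54 is the SD of change with equal variances, it is 54√((1+r)/2): 46.8 and 49.8. The range used covers both readings.

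With b = (480 − m)/s, the share of draws above the cap is 1 − Φ(b), and the mean falls by s·φ(b)/Φ(b). Worst case in this range, s = 54:

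- Active, m = 400: b = 1.48, share 6.9%, fall 54 × 0.1331/0.9308 = 7.72 min.
- Placebo, m = 380: b = 1.85, share 3.2%, fall 54 × 0.0718/0.9680 = 4.01 min.
- The contrast shrinks by 3.72 min per imputed value (unrounded).

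In the mildest case (s = 38.6, 340 against 360) the shrinkage is 0.10 min.

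- At 3.9% imputed: 0.10 × 0.039 = 0.004 to 3.72 × 0.039 = 0.145 min.
- At an assumed 10%: at most 0.37 min.
- Deliberately wide settings: 0.85 min with SD 54, means 400 against 420 and 15% imputed; 1.2 min with SD 80 instead.

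Under jump to reference both arms are drawn from the placebo model, so the shift largely cancels when missingness is similar.

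**Discard limit for sTST.** Imputed values per dataset at 10% missing: 900 × 0.10 × 2 = 180. Expected discards with every draw at the worst share: 180 × 0.0692/0.9308 = 13.4, well below 100.

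**The case against.** The strongest reply is that none of this matters for the result. The bounds act only on imputed values in sensitivity analyses, the sTST shift under MAR goes against the drug, and it is a fraction of a minute on the planning SD. That stands, and it sets the weight.

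The 480 may also be a deliberate nominal time in bed: SAP 12.6 applies it to another diary item when no sleep is reported ("sLSO is set as 480 minutes"). That shows a convention but gives no reason for using it as the ceiling for sTST. It is fair to add that 540 is not a hard limit either.

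On the code, the appendix text was machine-read and a lost character could explain the count. How the software treats a list of the wrong length was not tested. An unbounded Month 3 would also bring the run closer to the MMRM, which has no floor. It would still contradict 6.1.7.

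A reader might infer that observed weekly means above 480 are thrown away, including those resting on the minimum in SAP 10.1 ("subjects must have at least 2 days of data during each week"). The documents do not support this: 6.1.7 discards only intended imputed values. A reader might also infer that the tipping-point series loses its reference. It does not, because 15.5 carries its own delta = 0 run with matching lists.

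**Conclusion.** Minor, but wrong as written. Section 15.3 as printed does not implement 6.1.7, provided that entries are matched by position and the printed text equals the program. For LPS about 4–23% of active-arm Month 3 draws would then be negative, under assumed means and SDs. The sTST ceiling is borrowed from a different measurement. It costs 0.004–0.37 min of the sTST contrast at 3.9–10% missing, against a planned 20 min, under assumed arm means, SDs and missing fractions. A reader might infer that the efficacy conclusions are biased. They are not: the main MMRM uses no bounds and no conclusion is expected to change.

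Section 15.4 should not be taken as otherwise in order. Besides the spare entry, its Month 3 call omits Month 1 from the variable list, although 6.1.7 calls for the same sequential procedure with prior visits as predictors. That is a separate question for the sponsor.

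**What to change.** - Check the original program first.
- In SAP 15.3 use `minimum=. . 0 0 0 maximum=. . 480 480 480`, as in 15.5.
- In SAP 15.4 match each list to its variables. For the three variables as printed this is `minimum=. 0 0 maximum=. 480 480`, which also places a bound on baseline that the printed list leaves open. If Month 1 is added to the Month 3 call, four entries are needed.
- In SAP 6.1.7 give sTST its own upper bound, based on plausible diary time in bed and at least 540 min, or state why 480 is kept.
- State that the upper value in 15.2–15.5 depends on the endpoint: 480 for WASO and LPS, the sTST bound for sTST, 40 for IDSIQ.

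The cost is one or two sentences and a few characters of code, settled before unblinding, with no new data and no change to the main analysis.

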6.1.8 Supportive analyses

The main analysis performed for the primary and secondary efficacy endpoints [Section 6.1.4] will be repeated using the PPS to assess the effect protocol deviations may have on the results. Of note, these analyses rely on the MAR assumption.

The impact of any deviation from the assumption that the covariance structure is similar across treatment groups will be investigated by re-running the main analyses using two additional types of covariance structures. Firstly, the assumption of a common within-group standard deviation (SD) will be relaxed by using an unstructured covariance

matrix that is specific to each treatment group. Secondly, the more restrictive Toeplitz structure, shared across treatment groups, will be used. The Toeplitz structure requires fewer parameters to be estimated and will be considered as the main statistical analysis model if the model described in Section 6.1.4 fails to converge.

6.1.9 Subgroup analyses

Subgroup analyses for the primary and secondary efficacy endpoints will be performed to investigate the consistency of the treatment effect (i.e., ACT-541468 vs placebo) across subgroups defined by:

Age: < 65, ≥ 65 years
Sex: Male, female
Region: US, other (non-US)

The same model as for the main analysis (MMRM) will be fitted per subgroup. Of note, age group will not be included as a covariate in the model for subgroup analysis by age. Treatment effect estimates (LS mean plus 95% CI) will be presented via forest plots.

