4.2 Rationale for the selection of the study population

In this study, adult (18–64 years) and elderly (≥ 65 years) subjects with insomnia as defined by DSM-5 will be included [see definition in Section 1.1.1], unless subject's insomnia is associated with major comorbidities, especially comorbid neurological, affective or psychiatric disorders (e.g., severe or uncontrolled depression, anxiety or dementia) that may interfere with the efficacy and safety in the trial.

Elderly people exhibit a different sleep pattern to younger adults [Ohayon 2004] and the sensitivity of elderly and younger adults to the PD properties of a compound may therefore differ in the long term. Thus, randomization will be stratified by age in both pivotal studies to ensure that tested doses are given to a proportion of elderly subjects (i.e., 40% with age ≥ 65 years) and to ensure balance of the treatment groups within strata is achieved.

Concomitant pharmacological treatments for insomnia or concomitant CNS-related medications are not allowed in the study. This approach will favor optimizing the evaluation of the safety and efficacy profile of ACT-541468 by avoiding any potential confounding effects due to background co-medications.

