10.3.5 Subgroup analyses

Subgroup analyses will be conducted to explore the uniformity of the overall treatment effects with regards to efficacy and safety variables, and will be described in the SAP.

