10.5 Sample size

[figure not shown]
The assumptions used to calculate sample size are provided in [Table 2](#).

Table 2 Sample size assumptions for primary and secondary endpoints

Endpoint at Month 1 & Month 3	Expected mean difference compared to placebo	SD per treatment group	Effect size (mean/SD)
WASO	15	40	≈ 0.37
LPS	15	40	≈ 0.37
sTST	20	54	≈ 0.37
[REDACTED]	█	█	█

IDSIQ = Insomnia Daytime Symptoms and Impacts Questionnaire; LPS = Latency to Persistent Sleep; SD = standard deviation; sTST = subjective Total Sleep Time; WASO = Wake After Sleep Onset.

[figure not shown]
The assumptions for the between-subject SD per treatment group are based on two recently completed Phase 2 studies (AC-078A201, AC-078A202) conducted in adult and elderly populations receiving 5 mg, 10 mg, 25 mg, 50 mg ACT-541468 and/or placebo. The minimal clinically relevant difference compared to placebo in the mean change from baseline to Month 1 and Month 3 in WASO, LPS, and sTST is 15, 15 and 20 min, respectively.

Based on a two-sample z-test, at least 900 subjects randomized to 50 mg ACT-541468, 25 mg ACT-541468, and placebo in a 1:1:1 ratio (i.e., 300 per group) provides 98.9% power to detect an effect size of 0.37 for a single hypothesis test. This accounts for the Bonferroni correction [Section 10.3], where the significance level (alpha) is halved and set to 2.5% two-sided. However, as the number of null hypotheses (endpoints) to test increases, the power decreases, as shown in the figure below [Figure 3]. The power calculation in the figure assumes all null hypotheses are independent (a conservative assumption for power calculations) and the curves for N = 250 per group and N = 350 per group are included for

reference. Consequently, 900 subjects will provide at least 90% power to detect an effect size of 0.37 for testing 9 independent null hypotheses.

Figure 3 Effect of testing multiple null hypotheses on power at a given sample size

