A longitudinal data analysis method (i.e., linear mixed effects model) will be used for the analysis of change from baseline in WASO, LPS, sTST and IDSIQ Sleepiness domain score, separately.

The analysis model will adjust for the baseline value of the relevant response variable (either WASO, LPS, sTST or IDSIQ Sleepiness domain score), age group (< 65; \geq 65 years), treatment (higher dose; lower dose; placebo), visit (Month 1; Month 3), and the interaction of treatment by visit, and baseline by visit [see SAS[®] code in Section 15.1].

An unstructured covariance matrix, shared across treatment groups, will be used to model the correlation among repeated measurements. A restricted maximum likelihood approach will be used to derive (unbiased) estimates of variance components. The Kenward-Roger approximation will be used to compute the denominator degrees of freedom and adjust standard errors [Kenward 1997].

To evaluate the efficacy hypotheses, appropriate contrasts will be used to test the treatment differences of interest (i.e., the difference in least squares [LS] mean change from baseline between higher dose ACT-541468 vs placebo and lower dose ACT-541468 vs placebo, both at Month 1 and Month 3 [see Section 15.1]).

The LS mean for each treatment group per time point will be displayed along with associated standard errors and 95% confidence intervals (CIs). For each ACT-541468 dose level comparison with placebo, the placebo-adjusted LS mean will be displayed along with associated standard error, 95% CI and unadjusted two-sided p-value.

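### SAP 6.1.9 sets out to examine consistency of effect across age, sex and region, but the difference in effect between subgroups is never estimated

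*SAP*

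**What the plan says.** Protocol 10.3.5 states the aim and leaves the method to the SAP: "Subgroup analyses will be conducted to explore the uniformity of the overall treatment effects". SAP 6.1.9 repeats the aim for the primary and secondary endpoints, "to investigate the consistency of the treatment effect (i.e., ACT-541468 vs placebo) across subgroups" defined by age (under 65; 65 or over), sex, and region (US; other).

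The method is one sentence: "The same model as for the main analysis (MMRM) will be fitted per subgroup". So is the output: "Treatment effect estimates (LS mean plus 95% CI) will be presented via forest plots". The age-group covariate is dropped when the subgroup factor is age.

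Nothing elsewhere supplies a comparison between subgroups. The interactions in the main model (SAP 6.1.4) stop at "and the interaction of treatment by visit, and baseline by visit", and the SAS code in SAP 15.1 matches. SAP 6.1.6 adds descriptive summaries by age group, but these do not compare drug-placebo effects between the age groups.

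Age is not an incidental factor. Protocol 4.2 says that "the sensitivity of elderly and younger adults to the PD properties of a compound may therefore differ in the long term", and gives this as a reason for stratifying randomisation by age.

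**The concern.** Consistency is a statement about the difference between two treatment effects. The plan estimates each effect but not their difference, so its own question gets no estimate and no interval. Nor does the SAP say how the forest plot is to be judged.

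That leaves informal readings, and two are common. One is whether the subgroup CIs overlap. The other is whether one CI excludes zero while the other includes it. Neither tests or bounds the difference. The first is too slow to show a real difference. The second can suggest a difference where there is none, because the smaller subgroup has the wider interval. What is at stake is the wording of any consistency statement in the study report, above all for subjects aged 65 or over.

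**Working it through.** **Inputs**
- 300 per arm; SD 40 min and difference 15 min for WASO and LPS (Protocol 10.5 and Table 2). The minimal relevant difference "in WASO, LPS, and sTST is 15, 15 and 20 min, respectively". For sTST, 20/54 = 0.37 is almost the same ratio as 15/40, so the proportions below carry over approximately.
- About 40% aged 65 or over (Protocol 3.1): 0.4 × 300 = 120 per arm, leaving 180 per arm under 65.
- Normal approximation, no missing data, one dose at one visit.

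**The plan's own figure.** Protocol 10.5 states "300 per group) provides 98.9% power to detect an effect size of 0.37 for a single hypothesis test", at 2.5% two-sided. SE in SD units = √(2/300) = 0.0816; 0.37/0.0816 = 4.53; 4.53 − 2.24 = 2.29; power = 98.9%. It reproduces.

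**Standard errors by age**
- Under 65: 40 × √(2/180) = 4.22 min.
- 65 or over: 40 × √(2/120) = 5.16 min.
- Difference in effect: √(4.22² + 5.16²) = 6.67 min, so the 95% CI half-width is 1.96 × 6.67 = 13.1 min.

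**True effects 15 min (under 65) and 0 min (65 or over)**
- The two CIs separate only if the estimates differ by more than 1.96 × (4.22 + 5.16) = 18.4 min, which is more than the whole assumed effect.
- P(overlap) = Φ((18.4 − 15)/6.67) = 69%; a simulation gave 69.4%.
- P(direct contrast excludes zero) = Φ(15/6.67 − 1.96) = Φ(0.29) = 61%. Non-overlap occurs in the other 31%.
- P(under-65 CI excludes zero and 65-or-over CI includes it) = 0.945 × 0.95 = about 90%.

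**True effect 15 min in both strata**
- P(65-or-over CI includes zero) = Φ(1.96 − 15/5.16) = 17%.
- P(under-65 CI excludes zero and 65-or-over CI includes it) = 0.945 × 0.172 = 16%. The pattern that looks like loss of effect therefore also arises when the effects are equal.

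**How far the figures for 15 versus 0 min depend on the inputs**

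| Case | CIs overlap | Contrast excludes zero |
|---|---|---|
| SD 40, 60/40 split | 69% | 61% |
| SD 35, 60/40 | 57% | 73% |
| SD 30, 60/40 | 40% | 85% |
| SD 40, 60/40, 10% missing | 73% | 57% |
| SD 40, 50/50 | 68% | 63% |
| SD 40, 80/20 | 79% | 45% |

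The 50/50 to 80/20 range stands in for sex and region, whose splits the documents do not give. The lower SDs matter because the MMRM adjusts for baseline, which may bring the residual SD below 40.

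**The case against.** The strongest objection is to a claim that a reader might infer: that overlapping intervals will be taken as consistency, so that complete loss of effect in one subgroup would usually go unnoticed. The documents do not support it, for three reasons.

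- Neither document names overlap, or anything else, as the criterion. Readers can also compare point estimates.
- In the 15-versus-0 case the plot would show one interval clear of zero and the other including it in about 90% of trials, which few would call consistent.
- That case implies an overall effect of about 0.6 × 15 = 9 min. If the overall effect were the planned 15 min with none in the older stratum, the gap would be 15/0.6 = 25 min and the CIs would overlap only Φ((18.4 − 25)/6.67) = 16% of the time.

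Three further points are fair. The subgroups contain different subjects, so a reader can obtain the difference and an approximate SE from the plotted intervals; the number is unprinted, not lost. The analyses are exploratory and no decision in the plan depends on them. And the contrast is itself imprecise: it misses a 15-min difference 39% of the time.

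These points remove the alarming version and limit the weight of the concern. They do not supply the missing estimate. The pattern seen in 90% of trials when the effect is lost also appears in about 16% when it is equal, and the plan offers nothing to tell the two apart. That the difference can be derived by hand is a reason to print it.

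**Conclusion.** The concern holds as a gap in the analysis of a stated question: the plan asks about consistency, estimates no between-subgroup difference, and gives no rule for reading the display. That conclusion rests on the text alone and does not depend on the SD or on any scenario.

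The figures illustrate how unreliable the informal readings are. They rest on SD 40, a 60/40 age split, complete data and, for the 69%, a true 15-versus-0 contrast. They do not predict how the sponsor will read the plot, and neither document sets a miss rate against which to judge them.

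This is a worthwhile, low-cost improvement. It leaves the 16 tested hypotheses, the alpha allocation and the primary conclusions untouched.

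**What to change.** In SAP 6.1.9, for each of age, sex and region, add one MMRM on the whole FAS that extends the 6.1.4 model with subgroup, subgroup-by-visit, treatment-by-subgroup and treatment-by-subgroup-by-visit terms. Age group is already a main effect there, so age needs only the interactions. Beside each forest plot, report the difference in drug-placebo effect between subgroups with its 95% CI, by dose, visit and endpoint, labelled exploratory and unadjusted. State that any consistency statement will rest on that estimate and interval, and that a non-significant difference will not be read as proof of consistency.

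The cost is SAP wording and one extra model per factor and endpoint, with no new data and no alpha. There are three downsides to accept openly:
- The age interval is wide, about ±13 min, so the report may have to say that consistency is not established.
- There are 3 factors × 4 endpoints × 2 doses × 2 visits = 48 contrasts, of which about 48 × 0.05 = 2.4 would exclude zero by chance under full consistency.
- The pooled model shares its covariance matrix and baseline slopes across subgroups, so its contrast may differ slightly from the gap between the separately fitted estimates. A footnote should say so.
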